12.4. Pharmacokinetic Assessments

12.4.1. Blood Sample Collections

Blood collection may be performed using an existing line (arterial or venous noted on eCRF) at the start of the study (the use of EMLA[®] at the insertion site is permitted). If access for blood sampling is lost, a new line will only be established as part of the clinical management of the subject; otherwise, the subject's participation in the study will be early terminated. Procedures for blood draws should follow institutional SOC. All catheter lines should be appropriately flushed per institutional SOC prior to each blood draws. The discard volume must be restricted to 0.5 mL for tubing with a dead space of ≤ 0.5 mL and up to 1.0 mL for tubing with a dead space > 0.5 mL. Calculation and evaluation of the following pharmacokinetic variables will be performed for all subjects participating in study: (Single-Dose Phase: C_{max} , T_{max} , AUC_{0-t} , AUC_{0-24} , $AUC_{0-\infty}$, λ_n , $t_{1/2}$, CL/F [clearance], and V/F [volume of distribution]; Multiple-Dose Phase: C_{max} , T_{max} , AUC_{0-t} , λ_n , $t_{1/2}$, and CL/F; see [Table 7](#) for definitions). Blood samples (0.5 mL) will be obtained and placed into 2.0-mL dipotassium ethylenediaminetetraacetic acid (K₂EDTA) tubes at each blood collection time point for both phases (see [Table 3](#) and [Table 4](#)). The samples will be obtained at the following times:

- Single-Dose Phase: Serial blood will be collected at time 0 (Baseline), at 15 and 30 minutes, and at 1, 1.5, 2, 4, 6, 8, 12, and 24 hours post dose.
- Multiple-Dose Phase: Serial blood will be collected at: 0 (Baseline), at 0.5, 1, 1.5, and 2 hrs post-Dose 1, immediately prior to Doses 2, 3, 4, 5, 6, 7, and at 0.5, 1, 1.5, and 2 hrs post Dose 7.

Table 7: Pharmacokinetic Variables

Variable	Definition
C_{\max}	Maximum plasma concentration; the highest concentration observed during a dosage interval
T_{\max}	The time at which C_{\max} was observed
AUC_{0-t}	Area under the concentration versus time curve from time 0 to the last measured concentration (C_t) in the dosing interval, calculated by linear trapezoidal rule
$AUC_{0-\infty}$	Area under the concentration versus time curve from time 0 to infinity, calculated as $AUC_{0-t} + C_t/\lambda_n$
AUC_{0-24}	Area under the concentration versus time curve from time 0 to 24 hours (end of dosing interval)

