λ_n	Terminal rate constant, calculated as the negative slope of the ln-linear portion of the terminal plasma concentration-time curve
$t_{1/2}$	Terminal half-life, calculated as $\lambda_n/(\ln 2)$
CL/F	Apparent oral clearance, calculated as Dose/ $AUC_{0-\text{inf}}$ for single dose or Dose/ $AUC(0-\tau)$ for steady-state
V/F	Apparent volume of distribution, calculated as Dose/ $(AUC_{0-\text{inf}} * \lambda_n)$

Immediately after collection, the tube will be gently inverted several times to mix the anticoagulant with the blood sample. The plasma fraction will be separated by placing the collection tube into a refrigerated centrifuge (4°C to 8°C) for 10 minutes at 1,500 × g. The plasma fraction will be withdrawn by pipette and placed into a polypropylene freezing tube in 1 aliquot for subjects with body weights 3 to 6 kg and in 2 approximately equal aliquots for subjects with body weights greater than 6 kg. All sample collection and freezing tubes will be clearly labeled in a manner that identifies the subject and the collection time. Labels will be fixed to the freezing tubes in a manner that will prevent the label from becoming detached after freezing. All plasma samples will be placed into a freezer at –70°C or below within 1 hour after collection. The additional blood draws for the purposes of pharmacokinetic assessment in this study do not pose more than a minor risk to the subjects.

Total blood volume that will be collected for research purposes, including any discard volume, will be based on the age and weight criteria in section 12.4.2.

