13.6. Pharmacokinetic Analysis

Pharmacokinetic variables (Single-Dose Phase: C_{max} , T_{max} , C_{12} , AUC_{0-t} , AUC_{0-24} , $AUC_{0-\infty}$, λ_n , $t_{1/2}$, CL/F, and V/F; Multiple-Dose Phase: C_{max} , T_{max} , AUC_{0-t} , λ_n , $t_{1/2}$, CL/F, and V/F) will be estimated from the plasma concentration data using standard non-compartmental methods. Actual sample times, rather than scheduled times, will be used in the computation of pharmacokinetic parameters. Plasma concentrations below limit of quantification (BLQ) will be set to zero in the computation of mean concentration values; however, BLQ concentrations between 2 non-BLQ concentrations will be set to missing. For the computation of pharmacokinetic variables, the BLQ concentrations prior to the first measurable concentration

will be set to zero and other BLQ concentrations will be set to missing. The definitions and methods of determination for each pharmacokinetic variable are summarized in [Table 7](#).

Pharmacokinetic variables (CL/F , V/F , λ_n , and $t_{1/2}$, and dose normalized C_{max} , C_{12} , AUC_{0-24} , AUC_{0-t} , $AUC_{0-\infty}$) will be summarized by age group using N, mean, standard deviation (SD), geometric mean, CV, minimum, median, and maximum following dosing in the Single-Dose Phase and the first and third doses in the Multiple-Dose Phase. In addition, a 2-sided 95% CI will be constructed for both CL/F and V/F . T_{max} will be summarized by age group using median, minimum, and maximum.

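### Table 7 gives V/F only a single-dose formula, so any V/F calculated from a repeat-dose profile would be biased low; the sections also disagree on whether Multiple-Dose V/F is planned

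*Combined protocol and SAP*

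**What the plan says.** Table 7 defines clearance as "Apparent oral clearance, calculated as Dose" over AUC0-inf "for single dose or Dose/ $AUC(0-\tau)$ for steady-state". The next row is "Apparent volume of distribution, calculated as Dose" divided by the product of AUC0-inf and lambda_n, with no steady-state alternative. AUC0-inf is "Area under the concentration versus time curve from time 0 to infinity, calculated as" AUC0-t + Ct/lambda_n. Lambda_n is the "Terminal rate constant, calculated as the negative slope of the ln-linear portion of the terminal plasma concentration-time curve".

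The sections differ on whether Multiple-Dose V/F is wanted:

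- Section 13.6 ends its Multiple-Dose list with "CL/F, and V/F) will be estimated from the plasma concentration data using standard non-compartmental methods". The synopsis lists V/F there as well.
- Section 12.4.1, where Table 7 sits, ends its Multiple-Dose list with "and CL/F; see [Table 7](#) for definitions". V/F appears there only for the Single-Dose Phase.

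Section 13.6 refers to Table 7 for methods and summarises Multiple-Dose PK after Doses 1 and 3. It adds: "In addition, a 2-sided 95% CI will be constructed for both CL/F and V/F".

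**The concern.** The two forms in the CL/F row recognise that total area to infinity is the right denominator for one dose given alone, and area over one interval is the right one at steady state. The V/F row makes no such distinction. After a repeat dose, the area extrapolated to infinity includes drug left from earlier doses, yet it is divided into a single dose. The two rows then contradict each other: for the same child and dose, V/F no longer equals (CL/F)/lambda_n.

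V/F is one of only two parameters with a planned CI. A repeat-dose V/F well below the single-dose value could be read as a change in distribution on repeated dosing in children, when it would be ordinary accumulation. The bias also differs between 4 h and 6 h dosing, both of which are allowed, so it would add spurious variation between children.

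**Working it through.** The documents state no V/F value, half-life or accumulation factor, so there is no planned figure to reproduce. The check applies Table 7 to a known model.

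**Inputs from the protocol.** Dosing interval tau is 4 to 6 h (section 7). The formulas are those of Table 7. Multiple-Dose PK samples (sections 7.1.5 and 12.4.1) are taken at 0, 0.5, 1, 1.5 and 2 h for Dose 1, immediately before each of Doses 2 to 7, and at 0.5, 1, 1.5 and 2 h after Dose 7.

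**Assumed inputs.** Linear one-compartment kinetics, absorption rate ka = 3/h, half-life 2 to 10 h, and complete sampling over the interval with lambda_n equal to the true k.

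**Step 1, bolus-like input.** With r = exp(-k tau), AUC0-inf after Dose n divided by the single-dose AUC0-inf is (1 - r^n)/(1 - r). Table 7 therefore returns true V/F divided by this factor. Half-life 4 h and tau 4 h give r = 0.5. At Dose 7 the factor is (1 - 0.0078)/0.5 = 1.98; at Dose 3 it is (1 - 0.125)/0.5 = 1.75; at Dose 1 it is 1.00.

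**Step 2, oral input.** The factor becomes approximately [ka/(ka - k)] x [(1 - r^n)/(1 - r) - k/ka]. For the same case k = 0.1733, ka/(ka - k) = 1.0613 and k/ka = 0.0578.

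- Dose 7: 1.0613 x (1.984 - 0.058) = 2.04, so Table 7 gives 1/2.04 = 0.49 of true V/F.
- Dose 3: 1.0613 x (1.750 - 0.058) = 1.80, so Table 7 gives 0.56.

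**Step 3, the range.** Table 7 V/F as a fraction of true V/F, by numerical superposition:

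| Half-life | Dose 3, tau 4 h / 6 h | Dose 7, tau 4 h / 6 h |
|---|---|---|
| 2 h | 0.74 / 0.86 | 0.73 / 0.86 |
| 4 h | 0.56 / 0.66 | 0.49 / 0.63 |
| 6 h | 0.48 / 0.56 | 0.38 / 0.49 |
| 8 h | 0.45 / 0.51 | 0.31 / 0.41 |
| 10 h | 0.42 / 0.47 | 0.28 / 0.35 |

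At ka 1.5/h the Dose 7 range is 0.27 to 0.84, so with complete sampling the absorption assumption matters little.

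**Step 4, the steady-state form.** AUC(0-tau) after Dose n divided by the single-dose AUC0-inf is close to 1 - [ka/(ka - k)] r^n. Dose/(AUC(0-tau) x lambda_n) returns true V/F divided by that. The worst case is half-life 10 h with tau 4 h:

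- Dose 7: 1 - 1.024 x 0.144 = 0.853, or 1.17 times true V/F.
- Dose 3: 1 - 1.024 x 0.435 = 0.554, or 1.80 times true V/F.

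Over the whole grid the form gives 1.00 to 1.17 at Dose 7 and 1.00 to 1.80 at Dose 3.

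**Step 5, the samples actually planned.** After Dose 7 the last sample is at 2 h, and none is scheduled before Dose 8. Fitting lambda_n to 1, 1.5 and 2 h picks up the end of absorption and underestimates the slope. With half-lives of 2, 4 and 8 h and ka of 1.5 or 3/h, Table 7 V/F is then 0.33 to 1.21 of true. Extrapolating to tau, the steady-state form gives 1.18 to 1.48 times true V/F at ka 3/h (half-lives 2 to 10 h) and more than 2 times in every case at ka 1.5/h.

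**The case against.** The best defence is that Table 7 is consistent with its own section. Section 12.4.1 lists V/F for the Single-Dose Phase only, so a single-dose formula is all it needs. AUC0-inf is also absent from every Multiple-Dose estimation list; it appears only in the summary list of section 13.6 that covers both phases. This part stands: the documents conflict, and removing Multiple-Dose V/F from section 13.6 and the synopsis would be a legitimate repair. As written, however, the analysis section asks for V/F and names Table 7 as the method.

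A reader might infer that the trial will report a repeat-dose V/F that is too low. The documents do not support that. Section 13.6 summarises Doses 1 and 3. The formula is correct at Dose 1. Dose 3 has no post-dose profile, only the sample just before it and the next just before Dose 4. Dose 7 is the only repeat dose with serial samples and is not among the summarised doses. With samples to 2 h only, step 5 shows that even the direction of the net error is not assured there.

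A reader might also infer that the error equals the accumulation factor exactly. That holds only for one compartment with fast absorption, and at Dose 3 with a long half-life the accumulation reached is still well below its limit (bolus case, half-life 8 h, tau 4 h: 2.21 against 3.41).

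Finally, a reader might infer that adding the steady-state form settles the matter. Steps 4 and 5 show that it does not at Dose 3, nor at Dose 7 with the present samples.

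**Conclusion.** The point holds as a defect in the definition. Applied to a repeat-dose profile, Table 7 V/F is biased low by approximately the accumulation reached at that dose and is inconsistent with the CL/F row. The sizes, 0.28 to 0.86 of true V/F at Dose 7 and 0.42 to 0.86 at Dose 3, rest on assumed half-lives of 2 to 10 h, one compartment, ka 3/h and complete sampling. Under those conditions the direction does not depend on the half-life chosen. Single-Dose Phase and Dose 1 V/F are free of this error.

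Pharmacokinetics is a secondary objective, so this should be corrected but does not threaten the primary objective. Confidence is high in the algebra and in the conflict between sections, and lower in what would actually be reported after a repeat dose.

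**What to change.** 1. Reconcile section 12.4.1 with section 13.6 and the synopsis on whether V/F is a Multiple-Dose variable.
2. In Table 7, restrict Dose/(AUC0-inf x lambda_n) to a single dose: the Single-Dose Phase, and Dose 1 where it can be estimated.
3. If repeat-dose V/F is kept, define it as Dose/(AUC(0-tau) x lambda_n), that is (CL/F)/lambda_n, only at a dose where steady state is reasonable and the samples support both AUC(0-tau) and lambda_n. Otherwise report it as not estimable, and do not fall back on the single-dose formula. Do not use the steady-state form at Dose 3.
4. Alternatively, remove V/F from the Multiple-Dose lists in section 13.6 and the synopsis, to match section 12.4.1.

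The cost is one row of Table 7, the parameter lists and the PK program, with no added subjects or samples. The downside is that repeat-dose V/F may often be not estimable, because Dose 7 sampling stops at 2 h; correcting the formula does not supply the missing part of the curve.

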12.4.2. Blood Volumes

The total blood volume that will be collected for the study purposes will be limited to 3% (rounded to the nearest mL) of the total blood volume of the study subject based on Investigator feedback and values reviewed in Aladangady et al. and Howie). (24,25) This volume limitation includes discard volume, which should be limited to between 0.5mL to 1.0 mL depending upon the dead space of the blood collection tubing (see Appendix E footnotes). The blood volume of the study population is estimated to be 75 to 80 mL/kg. (25) The minimum age limit for participation in the study will be 2 years, which according to recent Center for Disease Control pediatric growth charts, has a minimum weight of approximately 10 kg (approximate lowest fifth

percentile weight for females).(26) Refer to [Appendix E](#) for required sample volumes for pharmacokinetic analyses.

12.4.3. Sample Storage and Shipment

All plasma samples will be stored frozen (at -70°C or below) until they are shipped to the analytical facility. Prior to shipping, the samples will be packed into thermal insulated containers and packed in sufficient dry ice to assure they remain frozen, and are protected from breakage during shipment. Samples will be shipped by overnight via priority courier. The samples will be divided into 2 shipments for subject with 2 aliquots, each containing 1 aliquot of plasma for each time point. The samples will be sent in 1 shipment for subjects with 1 aliquot (ie, 1 aliquot of plasma for each time point). After receipt of verification that the first shipment was received by the analytical facility, the second shipment (plasma) will be processed, if applicable.

Samples will be shipped in batches by age group and treatment cohort, for example, when the 0.05 mg/kg treatment cohort of 6 to ≤ 12 year olds has completed the Single-Dose Phase of the study, samples from all 6 subjects will be shipped from all sites (actual samples in 2 aliquots) and analyzed as a batch. For weeks containing a holiday, sites will contact the Sponsor for shipping instructions. The shipping address and contact information will be provided in a separate document.

12.4.4. Analytical Methodology

A validated microvolume liquid chromatography dual mass spectrometry (LC-MS/MS) analytical method will be used for the determination of the concentrations of oxymorphone and 6-OH-oxymorphone in the plasma samples. The microvolume assay will require 50 μL of plasma per sample. Details of the method validation and sample analysis will be included with the bioanalytical report (in the final clinical study report).

12.5. Clinical Laboratory Tests

Blood samples will be collected from subjects prior to dosing (baseline) and post dosing. Blood samples for baseline clinical laboratory tests may be collected at any time within 21 days prior to surgery. See sections [12.5.3](#) and [12.5.4](#) for the list of analytes to be included. Clinical labs drawn as part of the SOC (including the pre-operative and intraoperative period) will be acceptable for study purposes provided they are taken prior to first surgical incision and assessed by the Investigator prior to the first dose of study drug administration. Blood samples after dosing will be taken at 24 and 48 hours (or upon ET) post first dose in the Single- and Multiple-Dose Phases, respectively, and evaluated by the Investigator for clinical significance. Where possible, results from clinical laboratory tests performed as part of the SOC will be used for study purposes. A separate blood draw for the clinical laboratory test portion of this protocol will occur only if the clinical laboratory tests as part of the SOC will not be available to coincide with approximately the time scheduled by protocol or if clinical laboratory testing is not a part of SOC. All baseline test results must be available for review by the Investigator prior to first administration of study drug. Clinical laboratory test analytes listed in sections [12.5.3](#) and [12.5.4](#) will be entered into the eCRF.

12.5.1. Pregnancy Tests

Serum/urine pregnancy test ([serum] β hCG at Screening; subsequently, [urine] β hCG or per institution's SOC) will be completed as per [Table 3](#) and [Table 4](#).

12.5.2. Urine Drug Screen

Qualitative urine drug screen panel will include the following minimum set of analytes:

- Opioids, oxycodone, benzodiazepines, marijuana, cocaine, amphetamine, tricyclic antidepressants, and barbiturates

12.5.3. Chemistry

Chemistry panels may include analysis of the following analytes:

- alanine aminotransferase (ALT)
- aspartate aminotransferase (AST)
- bilirubin (total)
- blood urea nitrogen
- calcium
- creatinine
- glucose
- lactic dehydrogenase (LDH)
- inorganic phosphorus
- sodium
- potassium
- chloride
- total Carbon dioxide (CO₂)
- total protein
- albumin

12.5.4. Hematology

Hematology panels may include analysis of:

- hemoglobin
- hematocrit
- red blood cell count
- white blood cell count with differential
- platelet count

12.6. Vital Signs

Vital signs (respiratory rate, body temperature, heart rate, and blood pressure) will be taken at the screening visit, pre- or intraoperatively, at baseline, and at each specified time point during the Single- and Multiple-Dose Phases (see [Table 3](#) and [Table 4](#)). Blood pressure should always be taken in the same arm and when the subject has been supine for 5 minutes.

12.7. Physical Examination

A physical examination, including height and weight, will be conducted at Screening; a physical examination, excluding height and weight, will be conducted at the EOS/ET evaluation or early termination.

13. STATISTICS

13.1. Sample Size Consideration

The sample size of 6 subjects in each age group (A and B), treatment cohort, and study phase was selected to describe the safety, effectiveness and pharmacokinetic properties of the study drug in children aged 2 to ≤ 12 years. With up to 3 treatment cohorts and 6 subjects per treatment cohort, up to 18 subjects will be enrolled in each study phase. Assuming the %CVs for clearance and volume of distribution are both as high as 72% for pediatric subjects, then with 18 subjects per age group or 36 subjects per study phase, the 2-sided 95% confidence interval (CI) for both clearance and volume of distribution is $(0.71*X, 1.40*X)$, where X represents the geometric mean of either clearance or volume of distribution, respectively. In other words, with 18 subjects per age group or 36 subjects per study phase, the 2-sided 95% CIs are within 60% and 140% of the point estimates for the geometric mean estimates of both clearance and volume of distribution for oxymorphone in all age groups.

13.2. Analysis Populations

The safety population will include all subjects who take at least 1 dose of study drug. All safety analyses will be performed using this population. The effectiveness population will include all subjects who take at least 1 dose of study drug and who have completed at least 1 post dose pain intensity assessment. All effectiveness analyses will be performed using this population. All subjects who receive study drug as planned and have sufficient plasma concentration data to facilitate the calculation of pharmacokinetic variables will be evaluable for pharmacokinetic analysis. Final subject evaluability will be determined prior to locking the database.

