Record Surgical Details ^k		X													
Record food consumption ^l		X	Monitored Throughout Study												
Rescue medication ^m			As Needed Throughout Study												
Convert subject to discharge opioid of Investigator's choice													X		
Schedule 14-day follow-up call with site													X		
Study Completion															X

FOOTNOTES:

Abbreviations: BL=Baseline; EOS=End-of-Study; ET=Early Termination; IRB=Institutional Review Board; PK=Pharmacokinetic; Pre-Op=Preoperative; Intra-op=Intraoperative

- ^a Tests results must be available for assessment by the Investigator, or designee, prior to dosing a subject.
- ^b Investigator, or designee, will train/retrain subjects, parent(s)/legal guardian(s) on the proper use and completion of the pain assessments.
- ^c Investigator, or designee, will assess if the subject has the cognitive ability to correctly complete the required pain assessments.
- ^d Pregnancy test (for females of child-bearing potential only) must be completed and the result assessed prior to administration of study drug. Serum β hCG at screening; urine pregnancy test before study drug administration, except if screening occurs in hospital.
- ^e Blood sample drawn before dosing study drug.
- ^f Clinical labs drawn as part of the SOC will be acceptable for study purposes. Intraoperative labs are acceptable provided they are drawn prior to first surgical incision and assessed by the Investigator prior to administration of the first dose of study drug.
- ^g Captured following execution of informed consent/assent.
- ^h Collected by the Investigator for up to 14 days after the last dose of study drug (**documented telephone follow-up required**).
- ⁱ See [Appendix B](#) and section 9.3 for concomitant medication reporting.
- ^j A pain assessment will also be completed at the time of rescue immediately prior to rescue medication administration. **No pain assessments will be completed beyond rescue.**
- ^k Must include type of procedure(s), date of procedure(s), surgical start/stop time, and anesthesia/analgesia start and stop time.
- ^l Record all times that any food was consumed and what food was consumed (Diet-as-tolerated [DAT], DAT-soft, Full Fluids, Clear Fluids, water) by the subject from 1h prior to dosing through to EOS at 24h post 1st dose/ET

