7.1.3. Baseline Assessments and Procedures

Subjects who meet all inclusion/exclusion criteria will be enrolled into the study and assigned to receive a dose of oxymorphone HCl immediate-release oral liquid (study drug) based on order of enrollment.

Administration of the study drug will occur at the time postoperative parenteral analgesia is discontinued and oral dosing with opioid analgesics commences according to each institution's SOC. The subject's baseline level of pain will be assessed using an age-appropriate pain assessment instrument ([Appendix C](#), Faces Pain Scale-Revised [FPS-R]) or [Appendix D](#), the Face, Legs, Activity, Cry, Consolability scale [FLACC]).

The investigational staff will record the time, date, and dose of the study drug that the subject is administered in the source document and in the eCRF.

Baseline assessments and procedures will include the following:

- Assessing entry criteria: inclusion/exclusion criteria will be confirmed prior to beginning Baseline assessments/procedures.
- Retraining on completion of pain assessments: at Visit 2 before starting Baseline assessments and procedures.
- Obtaining urine pregnancy test: female subjects of child-bearing potential will be given a pregnancy test.
- Measuring vital signs: temperature, heart rate (beats per minute), respiratory rate (breaths per minute), and blood pressure (systolic and diastolic blood pressure, mmHg).

- Completing a respiratory assessment: see section 12.2 for the tests to be included in this assessment.
- Completing a neurological assessment: see section 12.3 and Appendix A for the test to be included in this assessment.
- Assessing current pain intensity (immediately prior to administration of study drug): each subject will provide a Baseline level of pain intensity using an age-appropriate pain assessment instrument (FPS-R for ages 6 to ≤ 12 ; FLACC for ages 2 to < 6 [see Appendix C and Appendix D, respectively]) prior to first dosing of study drug administration as well as just before each dose of study drug during the Multiple-Dose Phase; pain intensity scores will also be assessed just before taking the first rescue medication dose.
- Collecting a blood sample for pharmacokinetic assessment: draw prior to drug administration.
- Dosing the subject with study drug
 - The exact time when study drug was taken must be recorded. Any dose of study drug should not be administered for at least 2 hours following any opioid-based rescue medication.

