9.5. Rescue Medication

Subjects entering the study with non-oxycodone- or non-oxymorphone-containing, opioid-based PCA rescue medication will be allowed to continue to utilize their PCA rescue for as long as the device remains in place per institutional SOC. Oral rescue medication will also be allowed during the study, but also must NOT contain oxycodone or oxymorphone. Following completion of the study, subjects will be prescribed a rescue medication at the discretion of the Investigator, or designee, for BTP.

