11. ASSESSMENT OF EFFECTIVENESS

11.1. Pain Intensity

Subjects in the 6 to ≤ 12 year old group (Group A) will receive training on completing the self-report pain assessments; completion of the training will be documented in the source record. Each subject (ages 6 to ≤ 12 years) will assess his/her pain intensity at the designated times during the study (see [Table 3](#) and [Table 4](#)) using the FPS-R. The Investigator, or designee will conduct the pain assessments at the designated times during the study (see [Table 3](#) and [Table 4](#)) for subjects in age group 2 to < 6 years (Group B) using the FLACC; all pain scores in age group B will be recorded by the Investigator, or designee.

Current pain intensity will be collected at the following times during the study:

- Single-Dose Phase: Immediately prior to dosing; 15 minutes, 30 minutes, 1, 1.5, 2, 4, 6, 8, 12, and 24 hours post dose (or upon ET) or just prior to administration of rescue medication. Upon rescue, any remaining scheduled pain assessments will be discontinued.
- Multiple-Dose Phase: Immediately prior to first dosing; 0.5, 1, 1.5, and 2 hrs post-Dose 1, and immediately prior to all remaining Doses administered up through 48hrs after administration of the initial dose of study drug or until ET or just prior to administration of rescue medication. Upon rescue, any remaining scheduled pain assessments will be discontinued.

Selection of pain scales in children is complex because there is no single instrument suitable for all ages. While the use of a visual analog scale (VAS) is commonly employed in adults for the assessment of pain, the use of a VAS in young children is complicated by communication barriers. The selection of data collection instruments in this study is based on those with the widest acceptability and best evidence of psychometric properties regarding the appropriateness in the target population. The Pediatric Initiative on Methods, Measurement and Pain Assessment in Clinical Trials (Ped-IMPACT) recommended core outcome domains (including pain intensity) to be considered in clinical trials for acute and recurrent/chronic pain, which included the FPS-R and the Numerical Rating Scale (PI-NRS).⁽¹⁵⁾

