13.4. Effectiveness Analysis

The pain intensity difference (PID) at each post dose time point will be calculated as the pain intensity score at baseline minus the current pain intensity score at each post dose time point. Summary statistics of the pain intensity scores at each time point and PID at each post dose time point will be presented by pain assessment instrument, age group, treatment cohort, and study phase. For each subject, the PID over time will be transformed into a summary measure by calculating area under curve of PID (AUC_E) using the trapezoidal formula, adjusted for study duration. All time points before the first rescue medication will be used to calculate AUC_E . AUC_E will be analyzed by a heterogeneous analysis of variance (ANOVA) model with fixed effects for age group, treatment cohort, and the interaction of age group by treatment cohort for each study phase. The potential heterogeneity between the age-specific measurements will be assessed using a dummy variable for the difference in the statistical model. Least squared means of AUC_E for each combination of age groups and treatment cohorts and the corresponding 2-sided 95% CIs will be calculated based on the model.

Numbers and percentages of subjects who need rescue medication will be calculated by age group, treatment cohort, and study phase.

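### Rescue percentages default to a population that requires a post-dose pain score, so a child rescued early whose mandatory pre-rescue score is missed leaves both numerator and denominator

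*Combined protocol and SAP*

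**What the plan says.** Section 13.2 defines two populations that matter here. On safety: "The safety population will include all subjects who take at least 1 dose of study drug". The effectiveness population adds a condition, taking only dosed subjects "who have completed at least 1 post dose pain intensity assessment. All effectiveness analyses will be performed using this population".

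Section 13.4, Effectiveness Analysis, contains the rescue summary: "Numbers and percentages of subjects who need rescue medication will be calculated by age group, treatment cohort, and study phase". It names no population of its own. The Synopsis repeats both the populations and the rescue sentence. On the pain summary, 13.4 says: "All time points before the first rescue medication will be used to calculate" AUC_E. Section 13.7 allows no imputation of effectiveness data.

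On data collection, 11.1 says: "Upon rescue, any remaining scheduled pain assessments will be discontinued". Against that, Table 3 (footnote j) and Table 4 (footnote k) in section 7.1 state: "A pain assessment will also be completed at the time of rescue immediately prior to rescue medication administration". Section 7.1.3 adds that "pain intensity scores will also be assessed just before taking the first rescue medication dose", and 7.1.4, 7.1.5 and 11.1 carry the same requirement. The first scheduled post-dose score is at 15 minutes (7.1.4) or at 0.5 hours after Dose 1 (7.1.5).

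On PCA, 9.5 says that subjects who enter with a permitted opioid PCA "will be allowed to continue to utilize their PCA rescue for as long as the device remains in place per institutional SOC". Sections 7.1.4 and 7.1.5 count this as rescue.

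**The concern.** Needing rescue is a treatment failure that can be observed without any pain score, and the protocol already records it. Making the rescue percentage depend on a score ties it to a measurement it does not need. When that measurement is missing, the child removed is by construction one who was rescued very early.

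Scoring stops at rescue and nothing is imputed, so no later scheduled score brings the child back. The child has no AUC_E and is also absent from the rescue percentage, the one effectiveness summary that would have shown the failure. The distortion runs in one direction and favours the drug. Section 7 has the IDMC assess effectiveness before each escalation, and dosing recommendations are a secondary objective (6.2), so the cohort-level rescue rate should not depend on whether a score was captured.

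**Working it through.** The plan states no rescue rate, so there is no figure to reproduce. The check has three steps.

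**1. When is a rescued child lost?** Take a child rescued before the first scheduled score.

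- Pre-rescue score taken: it is a post-dose score, so the child meets the 13.2 definition, counts as rescued, and has one post-dose point for AUC_E. Nothing is lost.
- Pre-rescue score missed: scheduled scoring has ended (11.1; Tables 3 and 4) and nothing is imputed (13.7). The child is outside the effectiveness population, so is missing from the rescue numerator and denominator and has no AUC_E.

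The loss therefore needs a missed mandatory score. Section 9.5 lets PCA continue, and no section says how a score is obtained before a patient-triggered dose. That makes PCA a plausible route.

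**2. Effect on the rate.** Let n be dosed in a cell, x rescued, and m of those rescued unscored. The all-dosed rate is x/n and the effectiveness-population rate is (x − m)/(n − m). The difference is

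x/n − (x − m)/(n − m) = m(n − x) / [n(n − m)],

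which is never negative. With n = 6 (13.1) and m = 1 it is (6 − x)/30:

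| All dosed (exact 95% CI) | One unscored rescuer excluded (exact 95% CI) | Fall, points |
|---|---|---|
| 1/6 = 16.7% (0.4 to 64.1) | 0/5 = 0% (0 to 52.2) | 16.7 |
| 2/6 = 33.3% (4.3 to 77.7) | 1/5 = 20.0% (0.5 to 71.6) | 13.3 |
| 3/6 = 50.0% (11.8 to 88.2) | 2/5 = 40.0% (5.3 to 85.3) | 10.0 |
| 4/6 = 66.7% (22.3 to 95.7) | 3/5 = 60.0% (14.7 to 94.7) | 6.7 |
| 6/6 = 100% (54.1 to 100) | 5/5 = 100% (47.8 to 100) | 0 |

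Intervals are Clopper-Pearson, in percent. Losing two from 2/6 gives 0/4, a fall of 33.3 points, but that needs two missed mandatory scores in one cell.

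**3. How likely is it?** The documents give no PCA share, early rescue rate or missed-score rate. Let q be the assumed chance that a child is rescued before the first scheduled score and the pre-rescue score is missed. The chance of at least one such child among N is 1 − (1 − q)^N:

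| q (assumed) | Cell of 6 | One phase of 36 |
|---|---|---|
| 0 | 0% | 0% |
| 1% | 5.9% | 30.4% |
| 5% | 26.5% | 84.2% |
| 10% | 46.9% | 97.7% |

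**The case against.** The plan already guards against this. The pre-rescue score is required in both schedule tables and in four text sections, with no exemption for PCA, and the loss needs a departure from that rule. This stands, and it is why the point is minor.

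A reader might infer that a PCA press before the first scheduled score is enough to remove a child, or that a sizeable share of each cohort is at risk. The documents support neither. The pre-rescue score satisfies the population definition, and any estimated share would rest on PCA figures that the plan does not contain. Section 7.1.3 also has study drug given when parenteral analgesia is discontinued. On that reading early presses would be uncommon, although it sits poorly with 9.5. The documents do not say who operates the device for children aged 2 to <6 years.

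A reader might also infer that a child who stops early is lost in the same way. Sections 7.1.6 and 8.3 call for a pain score at early termination unless consent is withdrawn, so stopping early does not by itself remove a child.

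Nor would the child vanish from all reporting. Section 13.3.1 presents the size of each population, 13.3.3 tabulates concomitant medications in the safety population, and section 7 gives the IDMC individual data. These help, but none restores the rescue rate: 13.3.3 specifies no breakdown by cohort and no rescue category, and the note to Figure 1 keeps a rescued Single-Dose child in the study for all procedures except pain scores, so disposition need not show the event.

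Finally, the study is open-label and descriptive with 6 per cell and no test on rescue, and the intervals above are far wider than the shifts. That also stands.

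**Conclusion.** The point holds as a minor improvement. By default, the rescue percentages exclude any dosed child without a post-dose score. This matters only when a child is rescued before the first scheduled score and the mandatory pre-rescue score is missed. In that case exclusion is the wrong handling, and the rate can only fall or stay unchanged: one lost child in a cell of 6 costs between 0 and 16.7 points.

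The frequency is unknown. It is zero with perfect pre-rescue scoring. Under an assumed 1% to 10% rescued early and unscored, the chance of at least one case in a full phase of 36 is 30% to 98%. That range is an assumption, not an estimate, and the documents do not show that the loss will occur. The conclusion also relies on reading the rescue sentence in 13.4 as an effectiveness analysis under 13.2, which is the natural reading because no other denominator is named.

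**What to change.** - In 13.2, 13.4 and the Synopsis, state that the numbers and percentages needing rescue are computed in the safety population, that is, all dosed subjects.
- Keep the requirement for a post-dose score for PID and AUC_E only.
- Report, by age group, treatment cohort and study phase, the number of dosed subjects with no AUC_E because no post-dose score preceded rescue.
- Reconcile 7.1.3, on discontinuing parenteral analgesia when study drug starts, with 9.5, on continuing PCA, so that it is clear when a PCA dose counts as rescue.

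The first three changes cost about a sentence in each place, a changed denominator and one added count. Rescue use is already recorded under 7.1.4 and 7.1.5, so no new data are needed. For a child with no post-dose score, AUC_E stays undefined, but the child remains in the rescue rate: 2/6 is reported as 33.3% and not as 1/5, 20.0%.
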